## APPENDIX C: CYTOCHROME P450 INDUCERS

**Table 4 Cytochrome P450 Inducers**

	Strong	Moderate
CYP2C9 inducers	NA	Aprepitant, carbamazepine, enzalutamide, fosaprepitant , rifampin, ritonavir
CYP3A4 inducers	Carbamazepine, enzalutamide, mitotane, phenytoin, rifampin, St. John's wort	Bosentan, efavirenz, etravirine, modafinil
CYP = cytochrome P450; NA = not applicable. Source: https://www.fda.gov/Drugs/DevelopmentApprovalProcess/DevelopmentResources/DrugInteractionsLabeling/ucm093664.htm#inVivo

OLE	Open-Label Extension
PD	Pharmacodynamics
PK	Pharmacokinetics
PPS	Per-Protocol Analysis Set
PT	MedDRA Preferred Term
SAE	Serious adverse event
SAF	Safety Analysis Set
SAP	Statistical Analysis Plan
SMQ	Standardized MedDRA Query
SOC	MedDRA System Organ Class
TEAE	Treatment-Emergent Adverse Event
WHO	World Health Organization

Confidential

2. Introduction

This Statistical Analysis Plan (SAP) describes the statistical methodology and data handling for the clinical trial for Dova Pharmaceuticals with Protocol Number: AVA-CIT-330 (A Randomized, Double-Blind, Placebo-Controlled Study with an Open-Label Extension to Evaluate the Efficacy and Safety of Avatrombopag for the Treatment of Chemotherapy-Induced Thrombocytopenia in Subjects with Active Non-Hematological Cancers).

The ICH guideline E3 "Structure and Content of Clinical Study Reports" was used as a guide to the writing of the plan.

This SAP is based on the following study document(s):

- Clinical Study Protocol V2.0 (Amendment 1), 04 April 2019
- Electronic Case Report Form, dated 28 April 2020

3. Study Design and Objectives

3.1 Study Objectives

3.1.1 Primary Objective

The primary objective of this study is to evaluate the efficacy of avatrombopag in increasing platelet counts and therefore preventing the need for a platelet transfusion or chemotherapy dose reduction or delay in subjects with Chemotherapy-Induced Thrombocytopenia (CIT).

3.1.2 Secondary Objectives

The secondary objectives of this study are the following:

- To evaluate the safety of avatrombopag in subjects with CIT, and
- To investigate the effect of avatrombopag on bleeding in subjects with CIT.

[figure not shown]
3.2 Study Design

This is a Phase 3 randomized, double-blind, placebo-controlled study of the efficacy and safety of oral avatrombopag in subjects with CIT with active non-hematological cancers. The study consists of 4 periods: a Double-Blind Treatment Period, an Observational Period, an optional Open-Label Extension (OLE) Period, and a Long-Term Follow-Up Period, as described in Figure 1.

Confidential

Figure 1. Study Design

Chemo = chemotherapy; FU = follow-up; OLE = Open-Label Extension.

To be eligible for the study, subjects must have experienced thrombocytopenia during their current chemotherapy regimen as described in the inclusion criteria. The qualifying chemotherapy cycle is defined as "Cycle X". Subjects must be screened ≤ 28 days prior to the Baseline Visit, unless Screening and Baseline Visits are performed on the same day, and begin treatment during Cycle X.

3.2.1 Double-Blind Treatment Period

[figure not shown]
At the Baseline Visit, eligible subjects will be randomized in a 2:1 ratio to receive either avatrombopag or placebo in a double-blind manner prior to and during the subsequent chemotherapy cycle, Cycle X + 1. Randomization will be stratified by the number of chemotherapy agents the subject is receiving (1 or ≥ 2 permissible chemotherapy agents [nucleoside analog, including gemcitabine and fluorouracil; carboplatin or cisplatin; anthracycline; or alkylating agent]). Subjects will receive either avatrombopag or placebo once daily for 5 days prior to Chemotherapy Day in Cycle X + 1. Subjects will also receive avatrombopag or placebo once daily for 5 days immediately following Chemotherapy Day. Chemotherapy Day is defined per protocol as Day 1 to 3 of the subject's chemotherapy regimen (eg, if chemotherapy is given on Day 1 and Day 2, the second round of avatrombopag or placebo will start on Day 3). Avatrombopag or placebo will not be administered concurrently with chemotherapy on Chemotherapy Day. Chemotherapy regimens requiring dosing beyond Chemotherapy Day within the 21-day or 28-day cycle (eg, gemcitabine on Day 8) are allowed.

During the study, if the subject has a platelet count $>400 \times 10^9/L$, investigational product (IP) dosing will be stopped temporarily. Dosing may be restarted following discussion with the Medical Monitor.

Confidential

Figure 2. Treatment Schedule for Double-Blind Treatment Period

Chemo = chemotherapy; IP = investigational product.

3.2.2 Observational Period

Cycle X + 2 will be an Observational Period. The Observational Period is designed to enable assessment of whether the subjects meet the chemotherapy dose modifications or dose delay components of the composite primary endpoint while reducing decision-making bias for chemotherapy dose modifications or delays. Subjects in the Observational Period will not receive any IP pre- or post-Chemotherapy Day in Cycle X + 2.

For subjects not continuing into the optional OLE Period, a Follow-Up Visit will occur prior to (within 3 days) Chemotherapy Day in Cycle X + 3. For these subjects, their participation in the Observational Period will conclude after they complete the Follow-Up Visit and at that point they will enter the Long-Term Follow-Up Period (LTFU).

If Cycle X + 2 is the subject's last chemotherapy cycle, a Follow-Up Visit will occur at 30 days (± 3 days) after Chemotherapy Day in Cycle X + 2.

3.2.3 Optional Open-Label Extension Period

Subjects who complete the Double-Blind Treatment Period and the Observational Period will be eligible to enter an optional OLE Period at 5 days prior to Cycle X + 3, if they fulfill the inclusion criteria and do not meet any exclusion criteria for the optional OLE Period. Subjects must continue to fulfill the inclusion criteria and to not meet any exclusion criteria prior to pre-chemotherapy IP treatment in each enrolled open-label cycle to continue in the OLE Period.

All subjects will receive avatrombopag once daily for 5 days prior to Chemotherapy Day in Cycle X + 3. Subjects will also receive avatrombopag once daily for 5 days immediately following Chemotherapy Day. Avatrombopag will not be administered concurrently with chemotherapy on Chemotherapy Day.

During the study, if the subject has a platelet count $>400 \times 10^9/L$, IP dosing will be stopped temporarily. Dosing may be restarted following discussion with the Medical Monitor.

[figure not shown]
Subjects may repeat this treatment sequence and continue in the optional OLE Period until the end of their current chemotherapy regimen.

Confidential

Subjects will have a Follow-Up Visit at 30 days (± 3 days) after the last dose of IP treatment of the subject's last chemotherapy cycle.

Figure 3. Treatment Schedule for Optional Open-Label Extension Period

Chemo = chemotherapy; IP = investigational product.

3.2.4 Long-Term Follow-Up Period

After the Follow-Up Visit, all subjects will be contacted approximately every 6 months for up to 5 years by telephone during the LTFU Period for documentation of vital status (if death occurred, record of date of death) and occurrence of secondary malignancies.

3.2.5 End of Study

The end of study ("study completion") is defined as the date of the last protocol-specified visit/assessment (including telephone contact) for the last subject in the LTFU Period.

The study data will be cleaned and locked after the last subject finishes the Optional OLE Period. The study will then be unblinded and final analysis will be conducted. The data for LTFU Period will be reported once available.

3.3 Sample Size Justification

Assuming there is a 40% response rate in the active group and 10% in the placebo group, and using a 2:1 randomization, a 10% premature termination rate, and 90% power with 2-sided $\alpha = 0.05$, the sample size is 120 subjects (80 active subjects and 40 placebo subjects).

The assumptions for the response rates for the null and alternative hypotheses were based upon results from a study in CIT completed with oprelvekin (Neumega, Pfizer). The study design for oprelvekin was similar in that subjects were randomized to active or placebo following occurrence of severe thrombocytopenia (platelet count $\leq 20 \times 10^9/L$ in a previous cycle [Cycle X]). The primary endpoint of the study assessed the ability of oprelvekin to eliminate the need for platelet transfusions. In the placebo group ($n=30$), 93% of subjects required a platelet transfusion (7% responder rate) and 72% of active subjects ($n=29$) required a platelet transfusion (28% responder rate). The responder rates assumed for the null and alternative hypotheses in the AVA-CIT-330 study were based upon the responder rates in this similarly designed study with an assumption for a slightly

Confidential

higher response rate due to the inclusion of subjects with a platelet count in Cycle X of $<50 \times 10^9/L$, rather than $\leq 20 \times 10^9/L$.

4. General Analysis Definitions

4.1 Study Period and Visit Window Definitions

4.1.1 Study Periods

The study periods are defined as follows:

Screening Period: Starting the day of signature of informed consent up to and including the day before randomization. For subjects who are not randomized, the screening period will end on the day the subject is determined to be a screen failure.

Double-Blind Period: Starting the day of randomization up to and including the day before the start of chemotherapy in Cycle X + 2.

Observational Period: Starting the first day of chemotherapy in Cycle X + 2 up to and including the day before the pre-chemotherapy IP administration of Cycle X + 3 (if entering the OLE period) or the day of the Follow-Up visit (if not entering the OLE period).

OLE Period: Starting the first day of the pre-chemotherapy IP administration of Cycle X + 3 up to and including the day of the Follow-Up visit in the OLE Period.

Long-Term Follow-Up Period (LTFU): Starting the day after the Follow-Up visit, up to and including a period of 5 years or death, whichever occurs first.

4.1.2 Visit Windows

No formal visit windowing will be conducted. For by-visit/by-cycle tabular summaries, the scheduled visits or actual chemotherapy cycles will be used in the analyses. The exception to this is for nadir platelet counts; both scheduled and unscheduled platelet counts will be considered for designation of the nadir value within a cycle.

For analyses considering the worst post-baseline grade (laboratory shift tables) or post-baseline liver tests, all post-baseline values will be considered.

4.2 Definition of Populations

The analysis and reporting of the data from this study will be performed using the following analysis populations:

4.2.1 Full Analysis Set (FAS)

The FAS will include all randomized subjects.

4.2.2 Per-Protocol Analysis Set (PPS)

The PPS will include the subset of subjects from the FAS who do not meet the criteria that would potentially impact the evaluation of the efficacy endpoints. A full list of the criteria will be finalized prior to database lock and unblinding. Examples of these criteria may include:

- Use of certain prohibited concomitant medications
- Selected Inclusion/Exclusion criteria not met for the Double-Blind period

Confidential

- Lack of compliance with study medication during the Double-Blind period
- Study Discontinuation resulting in an inability to assess the primary efficacy endpoint
- Assigned to incorrect treatment (mis-randomization) or receiving incorrect study medication

4.2.3 Safety Analysis Set (SAF)

The SAF will include all subjects who receive at least one dose of IP.

4.3 Data Handling Conventions

4.3.1 General Conventions

Data will be analyzed using SAS (Version 9.4 or later). Descriptive analyses will be performed on baseline, safety, and efficacy data.

Descriptive statistics will be tabulated as follows:

- Categorical data will be summarized in contingency tables presenting frequencies and percentages, and
- Continuous data will be summarized using number of non-missing values (n), mean, standard deviation, median, minimum, and maximum values.

4.3.2 Platelet Counts

Platelet counts are collected at local laboratories for eligibility and efficacy assessments. Platelet count is also included in the hematology panel sent to the central laboratory as a safety evaluation. For the efficacy analyses, only platelet counts assessed by the local laboratories will be included in the calculations and summaries. For the safety analyses, only platelet counts assessed by the central laboratory will be included in the summaries.

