## 6 STUDY PROCEDURES

A schedule of procedures in tabular format is provided in [Table 1](#), [Table 2](#), and [Table 3](#) in [Appendix A](#).

Local laboratories may be used to determine study eligibility; however, for study analysis and reporting purposes, only values determined at a central laboratory will be used with the exception of platelet count. Platelet count analyses will be performed using local laboratory results. Local laboratories may be used if immediate results are clinically needed (eg, Baseline Visit).

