4.3.4 Definition of Baseline

For data displays for the Double-Blind/Observational Period, a baseline value will be the last non-missing value taken prior to the start of study treatment in the Double-Blind Period, unless otherwise indicated. For the efficacy analyses of platelet count, baseline will be defined as the lowest platelet count collected during the qualifying period in Cycle X and prior to the first dose of study drug.

For data displays for the OLE Period, a baseline value is the last non-missing value taken prior to the start of the pre-chemotherapy IP of Cycle X+3, unless otherwise indicated. For the efficacy analyses of platelet count, baseline will be defined as the lowest platelet count collected during Cycle X+2 and prior to the pre-chemotherapy IP of Cycle X+3.

Confidential

For data displays for the entire study (avatrombopag group only), a baseline value will be the last non-missing value taken prior to the start of study treatment in the Double-Blind Period, unless otherwise indicated. For the efficacy analyses of platelet count, baseline will be defined as the lowest platelet count collected during the qualifying period in Cycle X and prior to the first dose of study drug.

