4.4 Treatment Groups

Data displays for the Double-Blind Treatment period/Observational period will have columns for avatrombopag 60 mg dose and placebo groups, unless otherwise specified. Data displays for the optional OLE period will have 3 columns: subjects randomized to avatrombopag 60 mg dose, subjects randomized to placebo, and a total column (all subjects in the optional OLE period receive avatrombopag 60 mg). Data displays for the entire study will include subjects randomized to avatrombopag 60 mg only.

Data listings will generally include Subject ID, Age/Sex/Race, and an indicator of whether the applicable record occurred during the Screening, Double-Blind, Observational, or OLE periods.

5. Study Patients

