9.3 Clinical Laboratory Determination

Clinical safety laboratory assessments will include tests from the serum chemistry, hematology, and coagulation categories. Where applicable, laboratory values will be graded according to the NCI-CTCAE v5.0.

Local laboratories will be used to determine eligibility or when clinically needed; however, for the safety analysis of laboratory assessments, only laboratory values evaluated at a central laboratory will be used. Unless otherwise specified, all the summaries of the laboratory tests will be presented by the Double-blind period, OLE period, and entire study.

Shift tables of Baseline CTCAE grade to worst post-baseline CTCAE grade will be presented separately for gradable Hematology Parameters and Serum Chemistry Parameters. In the case of bi-directional toxicities, parameters will be presented separately (eg Calcium High, Calcium Low). For the purposes of tabulation, laboratory values which are not assigned NCI-CTCAE Grades 1, 2, 3, or 4 due to a toxicity will be assigned Grade 0 (within the normal range).

All laboratory data (including Hematology parameters, Chemistry parameters, Coagulation parameters, and pregnancy tests) will be included in separate laboratory listings.

A separate summary table for liver tests (ALT, AST, Alkaline Phosphatase, Direct Bilirubin, and Total Bilirubin) will be created. This table will indicate the number and percentage of subjects (presented by lab test) who have a highest post-baseline lab value for the test that is CTCAE Grades 1, 2, 3, or 4.

Observed values and changes from baseline for continuous Hematology and Serum Chemistry laboratory tests will be presented over time in box plots. Reference lines for the LLN and ULN will be included in the plots.

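### The central-laboratory-only rule leaves every scheduled mid-cycle platelet count out of the worst-grade safety table, though the effect stays within descriptive safety displays

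*SAP*

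**What the plan says.** SAP 4.3.2 assigns local platelet counts to efficacy and central counts to safety: "For the safety analyses, only platelet counts assessed by the central laboratory will be included in the summaries". SAP 9.3 applies the same central-only restriction to all safety laboratory data.

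SAP 9.3 then plans this display: "Shift tables of Baseline CTCAE grade to worst post-baseline CTCAE grade will be presented separately for gradable Hematology Parameters". It also plans box plots over time for hematology, with lines at the limits of normal. Platelets are part of the hematology panel (protocol Appendix B).

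SAP 4.1.2, in the section on visit windows, adds: "For analyses considering the worst post-baseline grade (laboratory shift tables) or post-baseline liver tests, all post-baseline values will be considered".

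The schedules (Appendix A of both documents, footnotes to Tables 1 to 3) send hematology to the central laboratory at Visits 1-5, 9, 13-15 and 17. Platelets are local only at Visits 6-8, 10-12 and 16.

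Protocol section 6 exempts platelet count from its central-only reporting rule and says: "Platelet count analyses will be performed using local laboratory results". Section 7 repeats the exemption.

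**The concern.** A table of worst post-baseline platelet grade should draw on the counts most likely to contain the worst grade. Here the scheduled counts between the end of post-chemotherapy dosing and the next cycle are all local, so the source rule removes them. SAP 4.1.2 does not restore them. It admits values from any visit, scheduled or not, but it does not change which laboratory counts. Under 4.3.2 it can add only unscheduled or Early Termination central samples.

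Adverse event tables do not fill the gap, because protocol 9.1.3 says thrombocytopenia should not be reported as an adverse event unless the investigator judges it caused by study drug.

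Two things are at stake. A reader may find a milder worst grade in the safety table than the nadir category for the same patients in the efficacy table. And the SAP uses a platelet source for safety that the protocol does not provide for.

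**Working it through.** The plan states no figure on this point to reproduce. The check is a cross-tabulation of visits by laboratory, followed by day arithmetic.

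**1. Scheduled counts after first dose, Double-Blind/Observational Period.** Visit 2 is the pre-dose baseline. Visit 12 applies only to patients on a 28-day cycle who do not enter the extension. Visit 13 is treated as the extension baseline.

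| Patients | Visits | Total | Local only | Excluded |
|---|---|---|---|---|
| 28-day, not entering extension | 3-12, 17 | 11 | 6, 7, 8, 10, 11, 12 | 6 of 11 |
| 21-day, not entering extension | 3-11, 17 | 10 | 6, 7, 8, 10, 11 | 5 of 10 |
| Entering extension | 3-11 | 9 | 6, 7, 8, 10, 11 | 5 of 9 |

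**2. Central gap in Cycle X+1.** Visit 5 = last chemotherapy day (1, 2 or 3) + 5 = Day 6 to 8. Visit 9, if chemotherapy is on time, = Day 22 or Day 29.
- 21-day cycle: 22 − 8 = 14 to 22 − 6 = 16 days.
- 28-day cycle: 29 − 8 = 21 to 29 − 6 = 23 days.

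**3. Central gap in Cycle X+2.** Visit 9 = Day 1. Visit 17 falls within 3 days before Cycle X+3, on Day 19-21 or Day 26-28. The gap is 18-20 days (21-day) or 25-27 days (28-day). For patients entering the extension, the next central sample is Visit 13 on Day 17 or 24, or one day earlier: 15-16 or 22-23 days.

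**4. Extension.** The first cycle has 3 post-baseline counts (Visits 14-16), each later cycle has 4, and Visit 17 adds 1. Over k cycles the total is 3 + 4(k − 1) + 1 = 4k, of which k are local only: 25%. From Visit 15 (Day 6-8) to the next central Visit 13.x (Day 17 or 24, one day earlier allowed):
- 21-day cycle: 16 − 8 = 8 to 17 − 6 = 11 days.
- 28-day cycle: 23 − 8 = 15 to 24 − 6 = 18 days.

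**5. Direction of the effect.** The worst grade over a subset of a patient's counts cannot be worse than the worst over all of them. Apart from differences between assays, the central-only table can match or understate, but not overstate.

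**6. Where the local counts do appear.**
- SAP 8.3: Cycle X+1 nadir and maximum categories by arm, up to Chemotherapy Day of Cycle X+2.
- SAP 8.2.1: platelet plots over time for the Double-Blind/Observational, extension and entire-study displays. These are in the efficacy section, so 4.3.2 gives them local counts.
- SAP 8.5: nadir per cycle in the extension, and similar summaries for the entire study in the avatrombopag arm only.

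No between-arm table covers the mid-cycle counts of Cycle X+2; only the plots do.

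**7. After the change.** The protocol's schedule footnotes pair a local count with the central sample at Visits 3, 4, 5, 9 and 17. A local-first rule therefore covers 11 of 11, 10 of 10 and 9 of 9 scheduled counts.

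**The case against.** The split by laboratory is deliberate and openly stated, and SAP 4.3.2 itself tells the reader why efficacy and safety platelet tables may differ. A low platelet count is the condition under study, so it is natural to report its depth under efficacy. SAP 8.3 does so with nadir bands from below 10 to at least 100 × 10⁹/L, and SAP 8.2.1 plots all periods. Bleeding and transfusions, with reasons, are tabulated in SAP 9.4.2 and 9.4.3. Table footnotes belong to a separate mock-table document that is not available here, so one cannot say the final displays will lack an explanation. A label on the table might be enough.

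Much of this stands and limits the point to descriptive safety displays. A reader might infer that mid-cycle counts are lost to the trial or that an efficacy result is affected; the SAP sections just named show otherwise. In the extension the loss is small: in 21-day cycles, when another cycle follows, the central Visit 13.x sample falls on Day 16-17, close to Day 15. In Cycle X+2, Visit 13 or Visit 17 similarly falls near Day 18 for 21-day patients.

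What does not stand is that a stated split makes the table right. A central laboratory cannot grade a sample it never receives. A label alone would still leave no worst-grade safety table with the mid-cycle counts, and would leave the departure from protocol section 6.

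A second inference concerns periods. SAP 9.3 says "all the summaries of the laboratory tests will be presented by the Double-blind period, OLE period, and entire study", and SAP 4.1.1 defines the Double-Blind Period as "Starting the day of randomization up to and including the day before the start of chemotherapy in Cycle X + 2". Read literally, Visit 9 and Cycle X+2 would leave the between-arm laboratory tables. SAP 4.3.4 and 4.4 use the combined period throughout, for example "Data displays for the Double-Blind Treatment period/Observational period will have columns for avatrombopag 60 mg dose and placebo groups", so the combined display is probably meant. This is a wording inconsistency, not evidence of planned omission.

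**Conclusion.** The point holds, at minor to moderate priority. Followed as written, the worst-grade platelet table and the platelet box plot omit about half of the scheduled counts after first dose in the Double-Blind/Observational Period, including all those in the 14-16 or 21-23 days after Visit 5 in Cycle X+1. The main thing missing is a worst-grade safety table that includes mid-cycle counts, above all any between-arm table for mid-Cycle X+2.

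This assumes undelayed cycles, counts scheduled visits only, and treats Visit 13 as the extension baseline. Unscheduled or Early Termination central samples could fill part of the gap. The size of any under-grading cannot be computed from the documents, and they do not show that any safety conclusion would change.

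**What to change.** - In SAP 4.3.2 and 9.3, except platelets from the central-only rule. Derive the worst post-baseline platelet grade from local counts, scheduled and unscheduled, using a central value only where no local count exists for that date. Take the shift-table baseline from the same source and say so.
- Apply the same source to the platelet box plot, or point the reader to the local-count plots in SAP 8.2.1.
- State that, where local reference ranges are not collected, one named reference range sets the Grade 0/1 boundary and the plot limits. The cut-offs that the protocol gives as absolute counts (75, 50 and 25 × 10⁹/L, in sections 1.2 and 4.2) do not depend on it.
- Keep the central-only table as a check, labelled as excluding the Day 11, 15 and 18 counts, with a cross-reference to SAP 8.3.
- In SAP 9.3, name the combined Double-Blind/Observational period.

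The cost is SAP wording, one derivation and a decision on reference ranges; no new data on platelet counts are needed. The downside is that counts come from several local laboratories rather than one assay, which the retained central-only table lets the reader check. Apart from dates filled by a central value, the main table would then follow protocol section 6.
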